#### **17.4.9 Time-to-Event Analyses**

Time-to-Event/Time-to-Decline analyses will be performed for a selected subset of endpoints as repeated measurements over time are needed. The distributions of time-to-decline in the key parameters will be summarized using the Kaplan-Meier method, with onset of decline defined as the first of two consecutive measurements that are worse than the baseline score, allowing for a certain margin which will be predefined in the SAP prior to database lock and unblinding; typical margins for the two primary endpoints are 1 unit. If there is no onset of decline prior to Week 52 and if Week 52 has a marked worsening as specified in the SAP for a given subject, an onset of decline will be triggered at Week 52 for that subject.

Time-to-decline will be calculated as date of onset of decline – date of randomization + 1.

The time-to-decline analyses are based on visit window. One measurement per visit window is selected, including off-treatment measurements. Subjects without any decline will be censored at the date of last assessment, but if a subject missed the scheduled visit, the subject is censored at the target day of the scheduled visit. The analysis will be run for the ITT population.

Any missing efficacy/imaging value for a scheduled visit will be treated as a worsening from baseline, for that visit. Because of this convention for missing values, it is possible that the first of two consecutive measurements that are worse than the baseline score by the defined amount occurs at a missed visit. In that case, since there is no date associated with the missed visit, the time-to-decline will be calculated based on the scheduled date of the missing visit.

The Cox proportional hazards regression model with effects for treatment group (two or three levels depending on whether primary or sensitivity comparison) and the randomization stratification variables will be used to compare LMTM 8 mg/day *versus* placebo (and LMTM 16 mg/day *versus* placebo, respectively) by way of Hazard Ratio, 95% confidence interval, and p-value (for alpha 0.05). A graph of the Kaplan-Meier estimates will be provided.

There will also be versions of this analysis using actual dates.

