#### 5.9.5. Time-to-event/Decline Analysis (Sensitivity)

This analysis, based on the ITTv5 population, will include off-treatment measurements (TOTOS) and will be done separately for the primary and secondary efficacy variables ADAS-cog11, ADCS-ADL23, and MRI whole brain volume. It will only compare subjects on HMTM 16 mg/day and control.

Time-to-event/decline will be calculated as date of onset of decline – date of first dose + 1 and will use only data from the double-blind treatment phase and upscaled values for the two co-primary endpoints.

Time of onset of decline is the first of two consecutive measurements with worsening, whereas worsening is defined as an impairment, with respect to the Baseline value of at least a change in units as outlined here:

- ADAS-cog11, ADCS-ADL23: 1
- MRI whole brain volume: 6,500 (mm^3 =  $\mu$ L)

If the threshold of the MRI whole brain volume does not appear to be reasonable once the unblinded randomization codes are used, these can be modified slightly (similarly if a model may not converge).

If the available Week 52 value (or the value of the last assessment in general, in case of early termination) is worsened without a prior worsening, an onset of decline will be triggered at Week 52 (or the respective last visit) for that subject. Subjects without any decline will be censored at the date

Sponsor:	TauRx Therapeutics Ltd.		
Protocol:	TRx-237-039		
Document Version No.:	3.0	Document Date:	07-JUN-2023

of last assessment, but if a subject missed the scheduled visit, the subject is censored at the target day of the scheduled visit.

Any missing efficacy/imaging value for a scheduled visit will be treated as a worsening from baseline, for that visit, but a single missing value at the last planned visit without a missing value or without a worsening in the previous visit will not count as a decline. If the time of onset is missing due to a missed scheduled visit the scheduled date of the missing visit will be used.

The Cox proportional hazards model with effects for treatment group and the randomization stratification variables will be used to compare HMTM 16 mg/day versus control by way of Hazard Ratio, 95% confidence interval, and p-value. A graph and a table of the Kaplan-Meier estimates will be provided.

Sample SAS code (will be fully validated at the analysis stage):

```
PROC PHREG DATA=dataset PLOTS(OVERLAY)=SURVIVAL;  

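### SAP 5.9.5 departs from protocol 17.4.9 on an unconfirmed Week 52 worsening: an isolated earlier worsening blocks the event, and the marked-worsening requirement is dropped

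*SAP*

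**What the plan says.** Both documents define onset of decline by confirmation. In SAP 5.9.5, "Time of onset of decline is the first of two consecutive measurements with worsening". The worsening margins are "ADAS-cog 11 , ADCS-ADL 23 : 1" and "MRI whole brain volume: 6,500" (mm³), measured from Baseline. Protocol 17.4.9 gives the same order of margin for the scales: "typical margins for the two primary endpoints are 1 unit".

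Week 52 is the last double-blind visit, so no later visit can confirm it. Protocol 17.4.9 covers this with two conditions: "If there is no onset of decline prior to Week 52 and if Week 52 has a marked worsening as specified in the SAP". SAP 5.9.5 has a single sentence for the same situation, under which a last value that "is worsened without a prior worsening, an onset of decline will be triggered at Week 52 (or the respective last visit) for that subject".

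SAP 5.9.5 also says: "Any missing efficacy/imaging value for a scheduled visit will be treated as a worsening from baseline, for that visit". The one exception is a lone missing value at the last planned visit when the visit before it was neither missing nor worsened. Protocol 17.4.5 adds that drop-outs are treated as having an event in the time-to-event models. SAP section 10, which lists changes to the planned analyses, does not mention the last-visit rule.

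**The concern.** Two things differ between the documents.

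**The condition.** The protocol asks whether an *onset of decline* has already occurred, meaning a confirmed pair. The SAP asks whether there has been a *worsening*, which it defines measurement by measurement. One isolated worsened visit is a worsening but not an onset. Read literally, it switches off the Week 52 trigger without creating an event of its own. The patient with more evidence of decline is then censored, and the patient with less is counted. Because a missed visit counts as a worsening, one missed early visit can block the trigger in the same way.

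**The threshold.** The protocol asks for more than an ordinary worsening before a single unconfirmed value counts, and leaves the figure to the SAP. The SAP gives none and reuses the ordinary margin.

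At stake are the event counts and Kaplan-Meier curves of an analysis that protocol 17.4.5 offers as evidence of robustness. The rule can also be programmed in two ways that give different counts.

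**Working it through.** **Plan figures.** Neither document gives an event count or power for time-to-decline, so there is nothing to reproduce for this analysis itself. The planning SDs used below can be checked against the power in SAP 5.3. With 200 × (1 − 0.25) = 150 per arm, the noncentrality parameter is δ/(σ√(2/150)).

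- ADCS-ADL23: 3.4/(8.5 × 0.1155) = 3.46, giving 93.2% power (stated 93.2%).
- ADAS-cog11: 2.6/(5.9 × 0.1155) = 3.82, giving 96.7% power (stated 96.7%).

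**Enumeration.** Write 1 for worsened and 0 for not worsened at Weeks 13, 26, 39 and 52. There are 2⁴ = 16 patterns. Apply each rule with the same margin.

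- SAP wording: an event if there are two consecutive 1s, or if Week 52 is 1 and all earlier visits are 0. This gives 9 of 16.
- Protocol condition: an event if there are two consecutive 1s, or if Week 52 is 1 with no earlier pair. This gives 11 of 16.
- The two patterns that differ are (1,0,0,1) and (0,1,0,1). Under the SAP wording both have no event, while (0,0,0,1) is an event.

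If the earlier worsening is at Week 39, the pair with Week 52 gives an event under both rules. Two consecutive earlier worsenings also give one under both. The size of the Week 52 change does not enter the SAP condition.

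**Illustrative size.** The planning inputs come from SAP 5.3: control decline and SD of 6.5 and 5.9 (ADAS-cog11), and 7.7 and 8.5 (ADCS-ADL23). Treated means are 6.5 − 2.6 = 3.9 and 7.7 − 3.4 = 4.3. Three things are assumed, because the documents do not give them: linear individual courses, no dropout, and an independent error SD e at Baseline and at each visit. The slope SD is √(SD² − 2e²), so the Week 52 change keeps the planning SD. There were 400,000 simulated patients per setting and the margin was 1 unit.

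| Scale, arm | e | Confirmed pair | Week 52 only | Week 52 plus isolated earlier | Events: SAP → protocol condition |
|---|---|---|---|---|---|
| ADAS-cog11 control | 2 | 78.7% | 3.3% | 3.2% | 82.0% → 85.2% |
| ADAS-cog11 control | 4 | 74.6% | 6.0% | 6.1% | 80.6% → 86.7% |
| ADAS-cog11 treated | 2 | 65.0% | 4.0% | 3.8% | 69.0% → 72.8% |
| ADAS-cog11 treated | 4 | 62.1% | 6.5% | 7.0% | 68.6% → 75.6% |
| ADCS-ADL23 control | 2 | 76.1% | 2.3% | 2.3% | 78.4% → 80.7% |
| ADCS-ADL23 control | 4 | 74.0% | 4.2% | 4.5% | 78.2% → 82.7% |
| ADCS-ADL23 treated | 2 | 62.9% | 2.8% | 2.7% | 65.7% → 68.4% |
| ADCS-ADL23 treated | 4 | 61.7% | 4.6% | 5.1% | 66.3% → 71.4% |

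The SAP event share is the confirmed column plus the Week 52 only column. The protocol condition adds the next column. At e = 5 the ADCS-ADL23 shift is about 6 points. Cox models fitted to the same simulated data under the two conditions gave hazard ratios differing by less than 0.01 in every setting.

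**The margin.** One unit is 1/5.9 = 0.17 of the planning SD of change for ADAS-cog11 and 1/8.5 = 0.12 for ADCS-ADL23. A patient with no true change shows at least 1 unit of worsening at a given visit with probability 1 − Φ(1/(e√2)): 36% at e = 2 and 43% at e = 4. The effect of a marked threshold cannot be computed, because neither document states one.

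**The case against.** The strongest reply is that this is a wording slip in a sensitivity analysis. *Prior worsening* may be shorthand for prior onset, only 2 of 16 patterns are affected, and the hazard ratio barely moves. The last two points are correct and set the weight of this finding. The first may be what was intended, but it is not what the text says, and a program follows the text.

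A second reply is that the protocol left *marked* to the SAP, so no protocol number is breached. That is also correct. But the word does nothing if it equals the ordinary margin, and dropping it is a change that section 10 should record.

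A reader might infer more than the documents support:

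- *Any earlier worsening blocks the Week 52 event.* It does not. Only an isolated, non-adjacent one (Week 13 or Week 26) does.
- *One unit is within test-retest noise.* Neither document gives a test-retest figure. The SDs of 5.9 and 8.5 describe 52-week change and include real differences in progression.
- *Extending the trigger to early terminators creates false events.* The next scheduled visit is then missing and counts as a worsening, so a worsened last value normally already forms a pair. Protocol 17.4.5 also treats drop-outs as events. Censoring those values would contradict both rules.
- *The treatment comparison is distorted.* The calculations do not show this.
- *The rule was altered after unblinding.* The SAP's modification history for version 3.0 lists no change to this analysis.

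**Conclusion.** The point holds as a departure from the protocol in two parts: a condition that excludes patients with an isolated, non-adjacent earlier worsening whatever their Week 52 value, and the loss of the marked-worsening requirement without a record in section 10. The first is a wrong rule as written, not merely a missing detail.

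The effect is modest. Correcting the condition alone adds about 3 to 7 percentage points of events per arm (2.3 and 2.7 points for ADCS-ADL23 at the smallest error SD), with a hazard ratio change below 0.01. These percentages rest on assumed error SDs of 2 to 5 units, linear decline and no dropout, and show size only. The enumeration needs none of those assumptions. The co-primary MMRM and its conclusions are unaffected.

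**What to change.** In SAP 5.9.5:

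1. Replace the no-prior-worsening condition with the protocol's: no onset of decline prior to Week 52.
2. Either state a numeric marked-worsening threshold for a single unconfirmed Week 52 value, larger than the ordinary margin for each endpoint and chosen and justified by the sponsor, or list its removal in section 10 as a change from the protocol.
3. Leave drop-out handling as in protocol 17.4.5 and keep the missing-visit rule. Do not censor worsened early-termination values.

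SAP version 3.0 postdates partial unblinding. The corrected analysis should therefore be labelled as such and reported beside the original.

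The cost is a few sentences of SAP text, one changed condition in the program and a second set of outputs. The first change can only add events. The net count after both changes depends on the threshold chosen.

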### 5.3. Sample Size Justification

Sample size estimations to achieve 90% power (two-sided alpha = 0.05) to detect a difference between HMTM 16 mg/day and true placebo have been performed for the two co-primary clinical endpoints. These assume a withdrawal rate of 20% to 25% over 52 weeks. The study sample size – here restricted to subjects randomized under protocol version 5.0 or higher as this is the primary analysis population – of approximately 450 subjects (approximately 200 subjects in each treatment group, with a further 50 subjects for secondary analyses of an HMTM 8 mg/day group) is based on the ADCS-ADL23 as a larger sample size is required to achieve the target power.

Based on an estimated decline in ADCS-ADL23 over 52 weeks in the control arm of 7.7 units with an estimated SD of 8.5 units, the study will have approximately 93.2% power (two-sided alpha=0.05) to detect a reduction in decline of 3.4 units or more. The 3.4 units are motivated by an estimated treatment effect of  $5.0 \pm 1.6$  (mean  $\pm$  standard error) units in the pooled studies TRx-237-005/ TRx-237-015.

Based on an estimated decline in ADAS-cog11 over 52 weeks based on pooled information from Studies TRx-237-005 / TRx-237-015 in the control arm of 6.5 units with an estimated SD of 5.9 units, 200 subjects per treatment arm provide approximately 96.7% power (two-sided alpha=0.05) to detect a reduction in decline of 2.6 units or more. The 2.6 units represent a conservative value as the estimated treatment effect based on pooled Studies TRx-237-005 / TRx-237-015 is  $5.2 \pm 1.3$  (mean  $\pm$  standard error) units.

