  CLASS subject treatment(REF='Control') severity(REF='moderate') region(REF='Europe')  
  prioruse(REF='None');  
  MODEL time *status(0) = treatment severity region prioruse;  
  ID subject;  
  RUN;
```

One version will be based on the visit windows (nominal data), and another will use actual dates (continuous data).

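### The visit-window version of the time-to-decline analysis has four possible event times but names no tie method; left at the PHREG default, its hazard ratio is pulled toward 1 and its test is far too conservative

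*SAP*

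**What the plan says.** SAP 5.9.5 converts ADAS-cog11, ADCS-ADL23 and whole brain volume into a time to decline for HMTM 16 mg/day against control. Onset is the first of two consecutive visits that are worse than Baseline by a set amount (1 unit on the two scales). A missing visit counts as worsening, with an exception for a lone missing last visit. A first worsening at the last visit also counts. A Cox model gives a hazard ratio, 95% confidence interval and p-value.

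On the time scale the SAP says "One version will be based on the visit windows (nominal data), and another will use actual dates (continuous data". The sample code is PROC PHREG with the statement "MODEL time *status(0) = treatment severity region prioruse" and no TIES= option. Neither document sets a tie method anywhere else.

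Protocol 17.4.9 takes the visit-window form as the base ("The time-to-decline analyses are based on visit window") and adds versions on actual dates. Protocol 17.4.5 lists time-to-event analyses among those meant to probe the robustness of the primary and secondary results. The SAP heading labels the analysis a sensitivity analysis, and no power is claimed for it.

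**The concern.** The scales are measured after Baseline only at Weeks 13, 26, 39 and 52, so the nominal version has four possible event times for about 400 subjects. The 1-unit threshold and the rule that missing means worse put many of the events at the first visit. The Breslow approximation is meant for data with few ties. It keeps all subjects who fail at a given visit in the risk set for every one of those failures. With heavy ties this shrinks the log hazard ratio and overstates its standard error.

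At stake is how the robustness table reads. The nominal version could show a hazard ratio too near 1 with a wide interval, next to an actual-dates version that looks stronger. A reader might take the gap for fragility of the treatment effect when it comes from a computing default.

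**Working it through.** **Inputs (SAP 5.3).** For ADCS-ADL23, decline "in the control arm of 7.7 units with an estimated SD of 8.5 units" and an effect of 3.4 units. For ADAS-cog11, "in the control arm of 6.5 units with an estimated SD of 5.9 units, 200 subjects per treatment arm provide approximately 96.7% power" and an effect of 2.6 units. Sample size is "approximately 200 subjects in each treatment group", withdrawal 20% to 25%, alpha 0.05 two-sided.

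**Step 1: reproduce the SAP's own power.** With 25% withdrawal, 200 × 0.75 = 150 per arm. The noncentrality is δ / (SD × √(2/150)), where √(2/150) = 0.1155.
- ADCS-ADL23: 3.4 / (8.5 × 0.1155) = 3.46; two-sample t-test power 93.2%.
- ADAS-cog11: 2.6 / (5.9 × 0.1155) = 3.82; power 96.7%.

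Both match SAP 5.3. They are powers for the Week 52 comparison, not for time to decline.

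**Step 2: why the ties matter.** At a visit with d events among n at risk in two equal arms, Breslow takes the information on the log hazard ratio as d/4 near no effect. The real (hypergeometric) variance of the score is (d/4) × (n − d)/(n − 1). One simulated setting (ADCS-ADL23, visit noise 40% of the Week 52 variance, 20% withdrawal) gave events in 46%, 16%, 11% and 7% of subjects at the four visits. For 400 subjects, ignoring censoring before Week 52:

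| Visit | n | d | (n − d)/(n − 1) |
|---|---|---|---|
| Week 13 | 400 | 184 | 0.541 |
| Week 26 | 216 | 64 | 0.707 |
| Week 39 | 152 | 44 | 0.715 |
| Week 52 | 108 | 28 | 0.748 |

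- Breslow information: 320/4 = 80; model SE = 1/√80 = 0.112.
- Real score variance: (99.6 + 45.3 + 31.5 + 20.9)/4 = 49.3; sampling SD of the Breslow estimate = √49.3/80 = 0.088.
- Variance ratio: 49.3/80 = 0.616. A nominal 1.96 cut-off acts like 1.96/√0.616 = 2.50, a two-sided level of about 1.3%.

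The simulation in that setting gave a model SE of 0.113 and an empirical SD of 0.088, in agreement.

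**Step 3: simulate the 5.9.5 rules.** The set-up was 200 per arm, SAP means and SDs at Week 52, linear mean decline, and a random slope plus visit noise. Visit noise was 20%, 40% or 60% of the Week 52 variance. Missing visits counted as worse. The Cox model had treatment, severity, region and prior use, with a two-sided Wald test at 0.05. The trajectories and noise shares are assumptions; the documents give no visit-wise means, variances or correlations. About 80% of subjects had an event, and 41% to 50% of all subjects had it at Week 13.

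Results with 40% noise (2,000 runs for the planning-effect and no-effect rows, 1,000 at half effect, 500 at the earlier-study effects, 250 on actual dates):

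| Setting | Withdrawal | Breslow HR, rejection | Efron HR, rejection | Loss (points) |
|---|---|---|---|---|
| ADAS-cog11, 2.6 units | 22.5% | 0.790, 58.4% | 0.741, 76.9% | 18.5 |
| ADCS-ADL23, 3.4 units | 22.5% | 0.802, 49.7% | 0.758, 69.6% | 19.9 |
| ADAS-cog11, half effect (1.3) | 20% | 0.893, 11.4% | 0.863, 25.4% | 14.0 |
| ADCS-ADL23, half effect (1.7) | 20% | 0.900, 8.8% | 0.875, 23.0% | 14.2 |
| ADAS-cog11, earlier-study effect (5.2) | 20% | 0.589, 100% | 0.522, 100% | 0 |
| ADCS-ADL23, earlier-study effect (5.0) | 20% | 0.710, 90.4% | 0.655, 96.0% | 5.6 |
| ADAS-cog11, no effect | 20% | 1.001, 0.5% | 1.001, 4.8% | n/a |
| ADCS-ADL23, no effect | 20% | 1.003, 0.9% | 1.004, 5.1% | n/a |
| ADAS-cog11, actual dates, 2.6 units | 20% | 0.739, 81.2% | 0.736, 82.0% | 0.8 |
| ADCS-ADL23, actual dates, 3.4 units | 20% | 0.755, 72.4% | 0.753, 73.2% | 0.8 |

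At the planning effects, over all three noise levels and 20% to 25% withdrawal, the loss is about 16 to 22 points; with no withdrawal it is about 12 to 15. Discrete logistic, complementary log-log and log-rank power agree with Efron within about 3 points, so Breslow is the outlier.

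**The case against.** The strongest reply is about weight. This is a labelled sensitivity analysis outside the primary test and outside the secondary sequence in SAP 5.9.3. It has no power target, and the error is conservative, so it cannot create a false positive. The same section also commits to an actual-dates version that hardly depends on the tie method. All of that stands. It limits the consequence but does not make the nominal hazard ratio, interval or p-value right.

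A second reply is that the code is only a sample, to be validated later. That carries less weight, because validation checks a program against its specification and the specification is silent on ties.

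Several stronger readings are tempting, and the documents do not support them:
- **The plan chose Breslow.** It names no method. That PHREG falls back on Breslow is a property of the software, not a statement in either document.
- **The loss is a fixed 20 points.** It depends on assumed trajectories and on the effect size, and disappears for ADAS-cog11 at 5.2 units.
- **The same loss applies to whole brain volume.** The tie structure is the same, but no MRI effect or SD is given for this comparison, so no size can be computed.
- **The adverse-event model in SAP 5.12.2 shares the defect.** It borrows this model, but its time runs in days from first dose to onset, and no comparable tie problem is shown.
- **The change has no downside.** SAP section 10 records that v3.0 followed the data snapshot of 28 April 2022 and partial unblinding. A change now moves the hazard ratio away from 1 and must be declared.

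**Conclusion.** The point holds for the nominal version on the two clinical scales. With four event times and no tie method named, use of the Breslow default gives a hazard ratio too close to 1, a model SE of about 0.11 where the true sampling SD is about 0.09, and a null rejection rate below 1%. The direction and the excess standard error follow from the tie structure and are confirmed by hand. The power loss of about 16 to 22 points is conditional on the SAP's planning effects, 20% to 25% withdrawal and assumed linear trajectories.

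A reader might infer that the trial's efficacy conclusion is at risk. It is not: the primary MMRM does not use this model, and the actual-dates version loses about 1 point. What is at risk is the reading of one robustness analysis. That is worth correcting because the correction is small.

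**What to change.** In SAP 5.9.5, for the nominal version, add TIES=EFRON or TIES=EXACT to the PHREG MODEL statement, or fit a grouped-time complementary log-log model with a visit effect. TIES=DISCRETE would also handle the ties, but it yields an odds ratio, which does not fit the stated hazard-ratio output. State the tie method in the text for both the nominal and actual-dates versions.

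The cost is one SAS option and one sentence, with no new data. Because the change would follow partial unblinding, record it in section 10 with its date and reason, and report the default-ties result next to the corrected one so that the reader can see the difference.
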